### **II. STUDY OBJECTIVE:**

Evaluate the impact of HAT therapy versus placebo in the treatment of patients with an acute NSTI and sepsis.

Primary outcome:

1. Hospital survival (including those who die within 24 hours of hospital admission)

Secondary outcomes:

1. Duration of vasopressor therapy
2. Requirement for renal replacement therapy in patients with Acute Kidney Injury (AKI)
3. ICU length of stay (LOS)
4. Change in serum procalcitonin (PCT) over first 72 hours
5. Change in SOFA score over first 72 hours (measured as SOFA score daily for four days, with day one being admission, then 3 days after, totaling 4 days of treatment with HAT)
6. Procalcitonin clearance (formula = initial PCT – 72 hour PCT divided by initial PCT x 100)
7. Number of wound related surgeries
8. Wound status at time of hospital discharge:
  - a. Open
  - b. Closed

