**Variables collected will include:**

- Patient name
- Medical record number (FIN)
- Date of birth
- Date and time of diagnosis of NSTI
- Date and time of randomization
- Time from diagnosis of NSTI and sepsis to initiation of HAT: hours.
- Time on pressors prior to initiation of HAT: hours
- Patient demographics (age, gender)
- Location of NSTI infection
  - Perineum
  - Genitalia
  - Groin
  - Lower extremity
  - Upper extremity
  - Hand
  - Foot
  - Head/Neck
  - Back
  - Chest
  - Abdomen
  - Multiple/Other – free text
- Preexisting conditions – similar to [name] study:
  - None
  - Diabetes mellitus
  - Hypertension
  - Heart failure
  - Malignancy
  - Chronic obstructive pulmonary disease
  - Cirrhosis
  - Cerebrovascular accident
  - Acute Kidney Injury (AKI)
  - Chronic kidney disease
  - Morbid obesity (weight and height)
  - Immunocompromised (HIV infection, neutropenia, post-transplantation, other)
  - Active medical systemic steroid use at baseline
  - Illicit drug use evident by patient history or drug screen
  - Active tobacco or nicotine product use
- Time from diagnosis of NSTI to surgery: hours

- Total number of visits to the operating room for NSTI-related surgical intervention
- Identification of NSTI derived from pressure-related injury
- Wound status at time of ICU discharge:
  - Open
  - Closed
- Duration of vasopressor therapy: hours cumulative from entire hospitalization
- Positive blood cultures (Y/N)
- Organism present on wound culture
- Time to antibiotic use
- Antibiotic used
- Requirement for renal replacement therapy in patients with AKI (Y/N)
- Procalcitonin level daily for 4 days (with day one being admission/enrollment, then 3 days after, totaling 4 days of treatment with HAT)
- Daily SOFA score for 4 days (with day one being admission/enrollment, then 3 days after, totaling 4 days of treatment with HAT)
- Total ventilator days
- ICU LOS: Days
- Hospital length of stay: Days
- Discharge disposition: alive or deceased
- If the patient withdrew: Y/N
- Reason for patient withdrawal: Free text

Population:

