be initiated per the randomization protocol, and only the pharmacy team will be unblinded. If the patient's legal representative signs the consent form on behalf of the patient, once the patient regains the ability to make medical decisions for themselves, they will be provided with the consent form and given the opportunity to continue in the study, signing a new consent themselves, or be given the option of discontinuing participation in the study. If the patient chooses to discontinue participation, all study data collected up to that point will be used in the study, although no new patient data will be collected, with the exception of any data needed to monitor the safety of the patient or adverse events in relation to the study treatments already administered.

Potential Risks to Subjects in the Study:

There exists the potential risk of a breach of subject confidentiality during the conduct of this research study. The following will be carried out to maintain patient confidentiality:

All medical information will be protected, and access will be limited to study investigators. Most of the data will be supplied from the electronic charting system at Ascension Via Christi Hospital – St. Francis Campus with patient identifiers (name, date of birth, medical record number [FIN]). The investigators will store data on an Ascension Google Drive. The research team is located in Room 3082 at Ascension Via Christi Hospitals on Saint Francis. The transfer will all occur within [contact] email system, with no one able to view the Google Drive without an Ascension email. No information will transfer outside this system.

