Patient identifiers will be kept with the participants PHI while the participant is hospitalized, and study data are actively being collected. Once the participant has been discharged, and all study data has been collected, subject identifiers (subject name, medical record number (FIN), date of birth, date of randomization, and date of procedures) will be maintained on a master list that links the subject to the specific study number. That list will be maintained under secure conditions at all times. Once all data has been deemed complete and analyzed and the work has been accepted for publication, the master list will be destroyed. This will effectively render the list de-identified as no other identifiers will be entered into the data set for analysis. The method in which this will be accomplished is that the master list will be shredded, and any computer file of the master list will be deleted from electronic media. The investigators and designated members of the research team will have access to the study data and will be responsible for data management.

Like any treatment there are potential risks with the administration of HAT, but these are overall low, as evidenced by numerous studies. The most recent large randomized control trial, VICTAS, which examined 501 patients, had no reported serious adverse events and only two adverse events (hemorrhagic shock and decreasing kidney function in the intervention group assessed as potentially related to study participation). In the 2017 Colliou et. al study, vitamin C-related oxalate nephropathy was seen in patients who received higher doses or received doses for a longer duration (1 month – 3 years) than [name] HAT dose. One trial found that hypernatremia was more common in the control group, which the study authors speculated might be due to increased sodium retention from glucocorticoids. GI bleed was another cited complication in this study with an incidence of 3:2 for treatment versus control groups. Like vitamin C, thiamine is a commonly used vitamin and can rarely cause electrolyte abnormalities. Administration of hydrocortisone, a low strength mineralocorticoid, is a commonly used medication in the ICU setting and can rarely cause hypertension or arrhythmia. The risk to

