omitting HAT has not been formally studied in this population. Finally, the treatment duration in our study will be limited (i.e. a maximum of 4 days for vitamin C and thiamine and 7 days plus a 3 day taper for hydrocortisone).

The potential risks due to septic shock from a NSTI itself are expected to be no different for patients whether they are enrolled in this study or not.

Evaluations During Treatment:

The evaluation period will begin at the time HAT or placebo is initiated after sepsis criteria is met and end at hospital discharge.

The investigators will collect data as outlined above under “Data Collection.”

Subject Non-evaluability:

Subjects will be deemed non-evaluable and will be dropped from the study if they meet the exclusion criteria and/or elect to withdraw from the study.

Costs

Participants will never be charged for study-related drugs in this study, regardless of the group to which they are randomized. This means that participation in this study will not cost participants more or less than the cost of normal care. No charges for care other than those that would be normally received will be incurred during the study and the cost for participants' normal care will be the participants' and/or the participants' insurance provider's responsibility.

Participants will not be charged for the drugs used in this study. The pharmacy will be absorbing the costs of the drugs regardless of whether it's thiamine, vitamin C, hydrocortisone, or placebo.

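### The named non-fatal harms of HAT, and kidney injury short of renal replacement, cannot be compared between arms from the variables the protocol lists

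*Combined protocol and SAP*

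**What the plan says.** **Risks named.** Section III, Potential Risks to Subjects in the Study, calls the risks of HAT low overall and then lists them.
- From the 501-patient randomised trial it reports "only two adverse events (hemorrhagic shock and decreasing kidney function in the intervention group assessed as potentially related to study participation".
- From a 2017 report it says that "vitamin C-related oxalate nephropathy was seen in patients who received higher doses or received doses for a longer duration" than the regimen used here.
- From another randomised trial: "One trial found that hypernatremia was more common in the control group", and "GI bleed was another cited complication in this study with an incidence of 3:2 for treatment versus control groups".
- It adds electrolyte abnormalities for thiamine, and hypertension or arrhythmia for hydrocortisone, all described as rare.

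**Data collected.** Under Evaluations During Treatment, "The investigators will collect data as outlined above under" the Data Collection heading. That heading refers to an attached spreadsheet and is followed by a list of variables. The list has no adverse-event item. Organ function is followed as "Daily SOFA score for 4 days (with day one being admission/enrollment, then 3 days after, totaling 4 days of treatment with HAT". Renal replacement in patients with acute kidney injury (AKI) is recorded as yes or no. Vasopressor hours over the whole stay, total ventilator days and survival to discharge are also recorded.

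**Objective and analysis.** The objective in Section II is to "Evaluate the impact of HAT therapy versus placebo in the treatment of patients with an acute NSTI and sepsis". None of the outcomes under it is a safety outcome, and Section VI describes no adverse-event summary.

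**Adverse events in this trial.** The one provision for collecting such data is under Patient Enrollment and Random Assignment. When a patient discontinues, data collection stops; the text qualifies this as follows: "with the exception of any data needed to monitor the safety of the patient or adverse events in relation to the study treatments already administered".

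**The concern.** The protocol identifies risks in advance and screens for some of them: the exclusion criteria remove patients with kidney stones, hyperoxaluria, oxalate nephropathy or G6PD deficiency. After randomisation, however, the listed variables give those risks nowhere to be recorded. The adverse-event wording covers only patients who stop, not those who stay in and receive the full course.

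Events that were not recorded during the trial cannot be compared at analysis. Section I justifies the study partly on the ground that HAT appears safe, and says that no known study has focused on necrotizing soft tissue infection. If the listed variables are all that is collected, an excess of GI bleeding, or of kidney injury that does not reach renal replacement, would leave no trace in the trial data. The assessment of impact promised in Section II would then cover benefit, death and severe organ failure, but not the other harms the protocol itself names.

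**Working it through.** **1. Risks set against the listed variables.** The risk text contains eight named items. Hypernatremia is itself an electrolyte abnormality, so there are 8 − 1 = 7 distinct risks.

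| Named risk | Nearest listed variable | Comparable between arms? |
|---|---|---|
| GI bleed | none | no |
| Hemorrhagic shock | vasopressor hours, which do not give the cause of shock | no |
| Decreasing kidney function | renal replacement (yes/no); SOFA on 4 days | only where it reaches renal replacement |
| Electrolyte disturbance, including hypernatremia | none | no |
| Hypertension | baseline condition only | no |
| Arrhythmia | none | no |
| Oxalate nephropathy (reported at higher or longer dosing) | renal replacement, without the cause | not identified |

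None of the seven has its own on-study field. AKI is listed as a preexisting condition and as a qualifier of renal replacement, not as a new event. The list asks for the SOFA score without an organ-by-organ breakdown, so kidney injury is not separately identified even on the scored days.

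**2. SOFA window against exposure.** Inputs are 4 scoring days (variable list), at most 4 days of vitamin C and thiamine, and 7 days plus a 3-day taper of hydrocortisone (Section III, Duration of Treatment and Potential Risks).
- Vitamin C and thiamine: 4/4 = 100%.
- Hydrocortisone before the taper: 4/7 = 57%.
- Hydrocortisone with the taper: 4/(7 + 3) = 40%.

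**3. The plan's own figure.** The documents give no figure for safety; the relevant one is 66 per arm (Section VII). Inputs are 20% against 4.24% mortality, two-sided α = 0.05 and 80% power. The mean rate is (0.20 + 0.0424)/2 = 0.1212.

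n = [1.960 √(2 × 0.1212 × 0.8788) + 0.842 √(0.20 × 0.80 + 0.0424 × 0.9576)]² / (0.20 − 0.0424)² = 1.642/0.02484 = 66.1

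Rounded up this is 67. Power at 66 per arm is 79.9%, so the stated size reproduces to within rounding.

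**4. What 66 per arm could say about harm if events were recorded.**
- Zero events in one arm: the one-sided 95% exact upper limit is 1 − 0.05^(1/66) = 4.4%. The upper end of a two-sided 95% interval is 1 − 0.025^(1/66) = 5.4%.
- Chance of at least one event in an arm, 1 − (1 − p)^66: 48%, 74%, 87% and 97% at true rates of 1%, 2%, 3% and 5%.
- Smallest increase detectable with 80% power, two-sided 0.05: from 2% to about 16%, 5% to about 21%, 10% to about 29%, and 20% to about 42%.

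The event rates in the last two lines are assumptions. The documents give none, and the 3:2 for GI bleed comes without denominators.

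**The case against.** Four objections carry weight.

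*Serious harm is already measured.* Death is the primary outcome, renal replacement and vasopressor duration are secondary outcomes, and ventilator days are recorded. All are collected in both arms, with no 4-day limit stated. This stands. A reader might infer that the trial cannot compare harm at all, or will end with no harm data by arm; the documents do not support that. What remains is narrower: none of these variables identifies a GI bleed, an electrolyte disturbance, hypertension, an arrhythmia or AKI managed without renal replacement.

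*The spreadsheet may hold the fields.* The variable list is worded as inclusive, and Data Collection defers to a spreadsheet that was not supplied. The discontinuation clause suggests that safety monitoring was intended. An adverse-event column therefore cannot be ruled out, and the point is conditional on that. A column alone would still leave the protocol text without a safety outcome, event definitions, a collection window for patients who stay in, or a summary by arm.

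*The risks are described as low, and SOFA covers the vitamin days.* Both are correct. Oxalate nephropathy is cited at higher or longer dosing, and a 40% coverage figure should not be read as applying to the whole regimen. Hydrocortisone exposure, to which the protocol attributes hypertension and arrhythmia, does run on after SOFA scoring ends.

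*The trial is too small for safety tests.* True, which is why a descriptive table is the right aim.

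The hypernatremia sentence might tempt a reader to discount the earlier safety evidence. It reports more events in controls but offers glucocorticoid sodium retention as the reason, although the cited trial's title places hydrocortisone in the treatment regimen. This is one sentence of background, to be checked against its source. It does not undermine the other studies cited.

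**Conclusion.** The point holds in limited form. Seven distinct risks are named, none has its own on-study field in the listed variables, and there is no safety outcome or adverse-event summary. Excess death or severe organ failure would be visible. The named non-fatal harms, and kidney injury short of renal replacement, could not be compared between arms from those variables.

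This rests on the protocol text alone and assumes that the unseen spreadsheet does not already carry the fields. The primary analysis and the sample size are unaffected. It is an inexpensive improvement to the safety information the trial yields, and the information gained would be descriptive, at the precision shown above.

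**What to change.** First check the spreadsheet. If the items are not there, add them to the variable list for both arms, from first dose to hospital discharge, abstracted by staff blinded to allocation:
- yes/no and date for GI bleed, hemorrhagic shock, new arrhythmia, new hypertension, clinically diagnosed oxalate nephropathy, new AKI after randomisation, and any serious adverse event, each with a short definition fixed in advance by the investigators;
- highest and lowest sodium and potassium, and highest creatinine, through day 10 where routine laboratory results exist (the documents do not say that such tests are done throughout);
- open-label steroid use, because Duration of Treatment allows steroids to be given to placebo patients. What was actually given could reveal the allocation, so the unblinded pharmacy should hold that record until analysis.

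Add a descriptive safety outcome to Section II and a matching sentence to Section VI: number and percentage of dosed patients with each event, by arm, with 95% confidence intervals and no hypothesis test. State that 66 per arm gives limited precision. Check the hypernatremia sentence against its source.

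Cost: thirteen items (7 events, 5 laboratory extremes and 1 steroid record), or 7 × 2 + 5 + 1 = 20 columns with event dates. Most come from the chart already being abstracted. The price is modest abstraction time and a short amendment, with no extra patients, visits or tests.

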#### Inclusion criteria:

1. Necrotizing soft tissue infection by clinical diagnosis and requiring surgical treatment.
2. Sepsis by clinical diagnosis and/or by Sepsis-3 criteria, with source attributed to the wound.
3. Anticipated or confirmed intensive care unit admission.

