#### Exclusion criteria:

Adapted from VICTAS protocol:

1. Age < 18 years of age
2. Weight < 40 kg
3. Prior enrollment in this study or current enrollment in another study of any kind
4. Surgical findings, pathology/histology findings, or other findings determined to be inconsistent with an infectious acute NSTI such that the clinical diagnosis is no longer that of a NSTI
5. Sepsis deemed unlikely
6. Limitations of care during enrollment [defined as refusal of cardiovascular and respiratory support modes described in inclusion criteria, including “do not intubate” (DNI) status and comfort care]
7. Known allergy or known contraindication to vitamin C, thiamine, or corticosteroids (including previous history or active diagnosis of primary hyperoxaluria and/or oxalate nephropathy, or known/suspected ethylene glycol ingestion, or known G6PD Deficiency)
8. Use of vitamin C at a dose of >1g/day (IV or oral) within the 24 hours preceding first episode of qualifying organ dysfunction during a given ED or ICU admission
9. Chronic disease/illness that, in the opinion of the site investigator, have an expected lifespan of < 30 days unrelated to current sepsis diagnosis (e.g., stage IV malignancy, neurodegenerative disease, etc.)

10. Kidney Stone(s) of any kind
11. History of Oxalate Kidney Stone(s)
12. Pregnancy or known active breastfeeding
13. Prisoner or Incarceration
14. Inability or unwillingness of subject or legal surrogate/representative to give written informed consent

Comparator:

Patients randomized to not receive HAT will comprise the control group and those randomized to receive HAT will comprise the treatment group.

Surgeons and surgical performance:

This study will not affect the surgical care of the patient. Patients with known/suspected NSTI will undergo surgery urgently/emergently as before. Patients who consent for and meet criteria for this study will be randomized, to either receive or not receive HAT. Care is otherwise identical for patients in each group. The only difference in the care of these patients will be in whether or not they receive HAT. The only surgeons who will be involved are those on the Burn service.

Study Site:

Ascension Via Christi Hospital – St. Francis Campus, Wichita, Kansas.

Duration of Treatment:

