Patients will be enrolled within 24 hours of diagnosis of sepsis related to a NSTI. HAT will be initiated within 4 hours of enrollment (thus treatment with HAT can occur no later than 28 hours from diagnosis).

Per [name] original study, HAT consists of:

- 1) 1.5 g vitamin C every 6 hours for 4 days or until ICU discharge
- 2) 50 mg hydrocortisone every 6 hours for 7 days or until ICU discharge (followed by a taper over 3 days)
- 3) 200 mg thiamine every 12 hours for 4 days or until ICU discharge

In our study, due to the prolonged ICU course typical of most patients with NSTIs, it is not felt feasible to continue indefinitely "until ICU discharge." Thus, treatment will be continued for 4 to 7 days plus a 3 day taper (respectively) as above, with no plan for a longer duration of treatment.

The control arm will receive the same standard ICU care for NSTI but will not receive HAT. They will receive a placebo consisting of normal saline, indistinguishable to the treatment team (blinded) but known to the pharmacy team (unblinded to treatment and placebo groups). This is so that if the treatment team elects to give stress dose steroids, they can be administered without breaking protocol (i.e. if the patient is getting HAT, it includes steroids, so if the treating team wanted to start hydrocortisone - because they didn't know if the patient was on HAT or placebo and felt steroids were indicated - the pharmacist could ensure the patient was on steroids one way or another without unblinding the providers).

Duration of Study:

The study enrollment period will continue for one year after its initiation, or until enrollment goal is met. Patients will be followed until hospital discharge.

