All adult patients presenting to Ascension Via Christi Hospital St Francis will be screened for inclusion and exclusion criteria. Once a potential study participant has been identified, a member of the study team will approach the patient or the patient's legal representative regarding inclusion into this study, and consent will be obtained. The length of the enrollment period of this study will be one year from the start of the study, or until the enrollment goal is met. Participants will be followed until hospital discharge.

Patient Enrollment and Random Assignment:

Patients who are admitted or diagnosed with sepsis secondary to an acute necrotizing soft tissue infection will be provided with the "Patient Informed Consent/HIPAA Authorization" document and will have the study explained to them during their initial evaluation by a member of the study team prior to enrollment. All qualifying patients who choose to participate in the study will sign the consent form, or have it signed by their legal representative. One copy of the consent form will be stored in the patient's chart and a second copy with the Research Scientist in the study files. A third copy of the consent will be provided to the patient for their reference. Randomization will be done via block randomization by the pharmacy department after a patient has consented to participate in the study.

The patient and/or his legal representative will have ample opportunity to decide whether they want to be included in this study and ask questions. The patient will be approached by a member of the study team prior to enrollment. This encounter will be within 24 hours of diagnosis, to provide ample time for consideration and to ask questions. Once consent is obtained, the HAT therapy should be started within 4 hours, such that the maximum possible time to initiation from diagnosis is 28 hours. If the patient meets inclusion criteria, then HAT or placebo (saline) will

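### The non-evaluability rule, naturally read, can remove randomised patients from the hospital-survival comparison, and no section names an analysis set

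*Combined protocol and SAP*

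**What the plan says.** All references are to the combined protocol and SAP.

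- **Entry** is on clinical grounds. Inclusion criterion 1 reads "Necrotizing soft tissue infection by clinical diagnosis and requiring surgical treatment".
- **Randomisation** follows consent: "Randomization will be done via block randomization by the pharmacy department after a patient has consented to participate in the study" (Patient Enrollment and Random Assignment).
- **Treatment** follows soon after: "HAT will be initiated within 4 hours of enrollment" (Duration of Treatment). No section requires operative or pathology findings before either step.
- **Exclusion 4** turns on such findings: "Surgical findings, pathology/histology findings, or other findings determined to be inconsistent with an infectious acute NSTI". Exclusion 5 applies where sepsis is judged improbable.
- **Subject Non-evaluability:** subjects are "deemed non-evaluable and will be dropped from the study if they meet the exclusion criteria and/or elect to withdraw".
- **Surrogate consent** (Patient Enrollment and Random Assignment): such patients are asked again "once the patient regains the ability to make medical decisions for themselves". Then: "If the patient chooses to discontinue participation, all study data collected up to that point will be used in the study". No new data follow, apart from safety data.
- **Section VI** assigns the chi-square test to categorical data. It names no analysis population and no handling of unknown survival status.
- **Section II** counts deaths within 24 hours of admission in the primary outcome. That defines an event, not a population.

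**The concern.** Exclusions 4 and 5 depend on judgements that can change once surgical, histological or later clinical information arrives. A patient can therefore be randomised, receive study drug and afterwards meet an exclusion. Withdrawal presupposes enrolment, so the rule clearly reaches enrolled patients. Calling such a patient non-evaluable and dropping them most naturally means they are not analysed.

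Hospital survival would then be compared in a subset formed after randomisation. Two analysts could also follow the plan faithfully and report different denominators, because the surrogate-consent paragraph keeps data that the non-evaluability paragraph appears to discard. If the choice is made after the arms are known, nobody can show that it was independent of the result.

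Only about 16 deaths are expected, so a few patients matter in a close result.

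**Working it through.** **1. Inputs.** Section VII: control mortality 20%, HAT mortality 4.24%, α 0.05, power 80%, 66 per arm. Section VI: two-tailed tests, significance at p ≤ 0.05. No removal rate is given, so every removal count below is an assumption.

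**2. The plan's own figure.** Pooled two-sided formula without continuity correction, with p̄ = (0.20 + 0.0424)/2 = 0.1212:

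n = [1.96·√(2 × 0.1212 × 0.8788) + 0.8416·√(0.20 × 0.80 + 0.0424 × 0.9576)]² / (0.20 − 0.0424)² = 66.1 per arm.

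Power at 66 per arm is 79.9%. The stated 66 is reproduced, so the sample size is not in error on its own inputs. Section VII mentions no allowance for dropped patients. Expected deaths are 66 × 0.20 = 13.2 and 66 × 0.0424 = 2.8, about 16 in all.

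**3. Balanced removal unrelated to arm or outcome.** Deaths per arm are binomial (n = 66). Deaths retained after removing k patients per arm at random are hypergeometric. All outcomes were enumerated with the uncorrected chi-square test.

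| Removed per arm (k) | Significance verdict differs from all-randomised, 20% vs 4.24% | Same, assumed 20% vs 8% |
|---|---|---|
| 1 (1.5%) | 1.5% of trials | 2.5% |
| 3 (4.5%) | 3.9% | 6.2% |
| 7 (10.6%) | 7.8% | 11.0% |

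- Exact power at the planned rates: 83.2% with all 66 per arm, 81.3% with 63 per arm (k = 3).
- Type I error at 20% in both arms: 4.9% with all randomised, 4.8% at k = 3, 5.3% at k = 7.

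**4. Removal related to outcome, chosen extremes.** Uncorrected chi-square, deaths/patients, control first.

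| Situation | Table | p |
|---|---|---|
| Near the planned rates | 13/66 vs 3/66 | 0.008 |
| Three control deaths dropped | 10/63 vs 3/66 | 0.033 |
| Four control deaths dropped | 9/62 vs 3/66 | 0.053 |
| Three HAT survivors dropped | 13/66 vs 3/63 | 0.010 |
| Borderline table | 13/66 vs 6/66 | 0.083 |
| Borderline, one HAT death dropped | 13/66 vs 5/65 | 0.046 |

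**5. Price of keeping everyone.** Suppose a fraction d of the HAT arm does not have the infection and dies at the control rate (an assumption). HAT mortality becomes 0.0424(1 − d) + 0.20d.

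| d | HAT mortality | Power at 66 per arm, normal approximation (exact) | n per arm for 80% |
|---|---|---|---|
| 0 | 4.24% | 79.9% (83.2%) | 66.1 |
| 5% | 5.03% | 74.4% (77.0%) | 75.5 |
| 10% | 5.82% | 68.5% (70.4%) | 86.5 |

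**The case against.** **The reading is an inference.** The rule mentions neither randomised patients nor a denominator. Dropping could mean ending participation, and meeting an exclusion could mean screen failure. Surgery is urgent while enrolment may come up to 24 hours after diagnosis, so operative findings may often precede randomisation. This stands as a limit on certainty: the frequency is unknown. It does not close the gap, since later pathology can still trigger exclusion 4 and no section says such patients are analysed.

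**Withdrawal is partly handled.** The specific surrogate-consent text could be read as governing the general rule. That covers one group only, and the conflict in wording remains.

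**The harm shown is small.** This stands. The random-removal model is also not the plan's mechanism: patients who withdraw or prove not to have the infection may differ in mortality. The discordance rates therefore illustrate sensitivity and do not estimate this rule's effect.

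**The one-patient change is selected.** This stands too. The borderline table was picked for being near the threshold, and section VI does not say whether chi-square is continuity-corrected. With correction, 13/66 vs 5/65 gives p = 0.082 and nothing flips; equally, 10/63 vs 3/66 moves from 0.033 to 0.065. A reader might infer that the trial's conclusion hangs on one patient. The documents do not support that as a general statement.

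**Another set would do.** A confirmed-infection set, specified in advance and adjudicated blind to arm, would also fill the gap. It would still depend on information arising after randomisation, so it is better as a sensitivity analysis.

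**Conclusion.** The point holds as a should-fix before unblinding. Naturally read, the plan permits removal of randomised patients from the hospital-survival comparison, gives conflicting data rules for one withdrawal group, and names no analysis set.

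The expected size is modest if removal is balanced and unrelated to arm or outcome: type I error about 5%, and about 2 points of exact power lost at an assumed three removals per arm. The planned 13 vs 3 deaths survives three dropped control deaths under the uncorrected test.

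A reader might go further and infer that the result will be biased, or biased towards HAT. The documents do not support that. They give no removal rate, and "only the pharmacy team will be unblinded", which makes arm-dependent removal less likely. Nor can bias be ruled out, because withdrawal and late exclusion need not be unrelated to outcome. For example, only a patient who lives long enough to regain capacity can leave by the surrogate-consent route. The priority rests on the rule setting the primary denominator, not on an expected large shift.

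**What to change.** 1. Add to section VI: the primary analysis of hospital survival includes all randomised patients in their assigned arm.
2. Add to Subject Non-evaluability: being deemed non-evaluable does not remove a randomised patient from that analysis.
3. Reconcile that paragraph with the surrogate-consent paragraph so that data collected up to withdrawal are used for every withdrawal. Rules on continued treatment or participation are for the sponsor to reconcile and are not touched here.
4. Use discharge disposition, already a listed variable, where consent permits, and report unknown outcomes by arm.

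A confirmed-infection sensitivity analysis, adjudicated blind to arm, is optional.

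**Cost.** Items 1 and 2 are one sentence each. Item 3 is a short edit. Item 4 needs no new variable but may need a consent line, because new non-safety data currently stop at discontinuation in the surrogate-consent group. The real downside is dilution: power of about 74% or 68%, against 80%, if an assumed 5% or 10% of the HAT arm had control-level mortality. No section supports a particular fraction or mortality for such patients, so restating the power is a matter for the sponsor if it expects many.
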